### 2.2 Secondary Endpoints

- All-cause mortality at 180 days.
- HF re-hospitalization at 180 days.
- Death or re-hospitalization from all causes at 180 days.
- Need for ICU admission during initial hospitalization.
- Acute coronary syndrome during initial hospitalization.
- Symptomatic hypotension during initial hospitalization.
- B-type natriuretic peptide (BNP) and creatinine level at 48 h and at discharge.
- Changes in circumferences of both legs and central venous pressure during hospitalization.
- Change in patient-assessed dyspnea at 48 h and prior to discharge.
- Blood pressure course over the first 6 days.
- Time to disappearance of a third heart sound (if present initially).
- Time to discharge.
- In-hospital days for HF at 180 days and 360 days.
- Total treatment cost at 180 days and 360 days.
- Functional status at 180 days and 360 days.
- Quality of life at 180 days and 360 days.
- Fractures due to falls within 180 days and 360 days.
- Death or HF re-hospitalization at 360 days.

Predefined subgroup analyses will be performed in patients younger or older than 75 years of age, men and women, systolic (LVEF < 45%) HF and HF with preserved LVEF, systolic blood pressure at presentation lower or higher than 140 mm Hg, coronary artery disease present or not, BNP levels lower or higher than 1000 pg/ml and isolated or concurrent right HF.

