### **8.2 Statistical Analysis**

The statistical analyses will be performed using the SPSS / PC (version 14.0, SPSS Inc., USA) software package. A statistical significance level (p-value) of 0.05 will be used. All data will be analyzed on an intention-to-treat basis. Comparisons will be made using the t-test, Mann Whitney U-test, Fisher's exact test, survival analysis (Kaplan Meier method), Cox regression analysis and chi-square test as appropriate. All hypothesis testing will be two-tailed. Statistical support will be performed by [name] from the Institute of Social and Preventive Medicine of the University of Basel.

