### **f. Sample size**

Sample size calculation is based on the on the data from the BASEL V study. A hypothesized 20%-decrease of the composite endpoint death or HF re-hospitalization at 180 days, will require 385 patients per treatment arm to obtain, with a probability of 80%, a log rank test result that is statistically significant at the 5%-level. In order to compensate for an expected 1-2% of patients in whom the primary endpoint could not be assessed at 180 days due to loss to follow-up or complete withdrawal of ICF, it was planned to enroll approximately 780 patients.

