#### **3.1. Randomization**

Group assignment was accomplished with the use of a computer-generated randomization scheme in a 1:1 ratio. Randomization will be stratified for enrolling site and the severity of HF as quantified by the BNP level (below or above 1000 ng/l) or NTpro-BNP level (below or above 4000 ng/l). Patients will be randomized to either the early goal directed group or the control group.

---

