22 Six days after admission or until discharge from the index hospitalization.

23 **iii. Dose of exposure and concentration**

- 24 – sublingual nitrates: 0.8 mg glyceryl trinitrate, sublingual, 3 times every ten minutes.
- 25 Sublingual nitrates have an approximate onset of action of 1-3 minutes and a half-life
- 26 of 1–4 min.
- 27 – hydralazine 25 mg p.o. four times a day (QID) for 2 days. Half-life, 2–8 hours,
- 28 – nitroglycerin patches in a dosage between 40 to 80 mg in 24 h depending on systolic
- 29 blood pressure and for 5 days. Elimination half-life takes around 10 minutes.
- 30

31

32

33 **9. Evaluation of patients at follow-up**

34 Patient are contacted at 90, 180 and 360 days follow-up (telephone calls, letters). During the  
35 FU patients will be asked about current medication, functional NYHA class and additionally,  
36 to complete Quality of life (EQ-5D-3L) and Kansas City Cardiomyopathy Questionnaire  
37 (KCCQ).

38 **aa. Follow-up at 90 days**

39 The follow-up 90 days months contains a self-reported medicament list update, potential  
40 endpoints assessment, a functional NYHA class assessment and Quality of Life (EQ-5D-3L)  
41 assessment.

42 **bb. Follow-up at 180 days**

43 The follow-up 180 days months contains a self-reported medicament list update, potential  
44 endpoints assessment, a functional NYHA class assessment and Quality of Life (EQ-5D-3L)  
45 and KCCQ assessment.

46 **cc. Follow-up at 360 days**

47 The follow-up 360 days months contains a self-reported medicament list update, a functional  
48 NYHA class assessment and Quality of Life (EQ-5D-3L) and KCCQ assessment.

49 .

50

51 **10. Evaluation of efficacy parameters**

52 **dd. Analysis of primary, secondary, and other efficacy endpoints**

53 **i. Analysis of primary endpoint**

54 The primary endpoint will be analyzed using survival analysis for cumulative incidence (e.g.  
55 Cox regression, Kaplan-Meier and Hazard Ratio) and log rank testing for significance at 180  
56 days.

57 **ii. Analysis of secondary endpoints**

58 Secondary endpoints will be analyzed using the same approach as for the Primary endpoints  
59 and interaction test (p-value) will be conducted between the treatment group and the sub-  
60 group variables.

61 **iii. Analysis of other endpoints**

62 All other endpoints, including novel biomarkers or neurohormones not yet specified in the  
63 protocol will be analyzed using the same approach as for the **Secondary endpoints**.

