**v. Sensitivity Analyses of endpoints**

To deal with missing data in the baseline assessment of the endpoint and to deal with missing data of the follow-up assessment of the endpoint, sensitivity analyses will be conducted, where missing follow-up values and baseline values will be multiple imputed using chained equations.

The missing data for the primary and secondary endpoints (as applicable what is actually missing, including baseline and follow-ups) are imputed using chained equations, 20 data-sets will be created. The equations include the baseline clinical characteristics, the non-missing primary from the previous follow-up assessment (baseline if none available). Endpoints are taken from baseline and all the follow-ups, as applicable (typically baseline, 180 days and 360 days).

Afterwards all sensitivity analyses are conducted on the 20 data-sets for the composite endpoint, The sensitivity analyses will be shown in the Supplementary Material following the same structure as the Tables 3 – 5.

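### The SAP gives no rule for death in the non-fatal secondary endpoints, and its default methods overstate HF readmission, cut hospital days short and allow imputation after death

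*Combined protocol and SAP*

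**What the plan says.** Section numbers follow the SAP's table of contents.

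- **Method for secondary endpoints (SAP 10.1.2).** "Secondary endpoints will be analyzed using the same approach as for the Primary endpoints". SAP 10.1.1 describes that approach as survival analysis for cumulative incidence (Cox, Kaplan-Meier, hazard ratio) with a log-rank test at 180 days.
- **Endpoints concerned (Protocol 2.2, SAP 2.2).** HF re-hospitalisation alone at 180 days; time to discharge; "In-hospital days for HF at 180 days and 360 days"; functional status and quality of life at 180 and 360 days.
- **Methods by data type (SAP 10.2).** Counts go to a chi-squared test, continuous data to Mann-Whitney, and time-to-event data to Cox. None of these allows for time alive or names a competing-risk method.
- **Censoring and last assessment (SAP 5.3, 6.6.5).** The censoring rule is written for the primary endpoint. The last-assessment rule lists withdrawal and loss to follow-up. Neither mentions death.
- **Imputation (SAP 10.1.5).** "sensitivity analyses will be conducted, where missing follow-up values and baseline values will be multiple imputed using chained equations". The rule covers primary and secondary endpoints, uses 20 data sets, and has no exception for values that are absent because the patient died.
- **Status (SAP 6.6.4).** Secondary analyses are exploratory and their p-values are not read against a threshold.

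**The concern.** A method that suits a composite containing death does not carry over unchanged to an endpoint that death prevents. For HF re-hospitalisation alone, the primary approach leaves death as censoring. Kaplan-Meier then treats patients who died as if they could still be readmitted, so its complement is not the cumulative incidence that the SAP says it reports. For in-hospital HF days the mechanism is truncation: a patient who dies early can accrue few days. Quality of life and functional status do not exist after death, yet the imputation rule as worded can supply them.

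The protocol's introduction predicts reduced time to discharge and a better clinical and economic outcome, and its risk section names hypotension with reduced organ blood flow as the main potential harm. Readmission, stay, hospital days and quality of life are the endpoints a reader would use to judge the first set of claims. Deaths should not enter them by accident of the default method.

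**Working it through.** The plan states no figure for these endpoints, so there is none to reproduce. Its sample size of 385 per arm concerns the composite and is not in question here.

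**1. How many deaths to expect.** The documents' only mortality figure is 50% at three years (Protocol, Summary and Introduction). Assuming a constant hazard over 1,095 days:
- 180 days: 1 − 0.5^(180/1095) = 0.108, or about 83 of 770.
- 360 days: 1 − 0.5^(360/1095) = 0.204, or about 157 of 770.

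**2. HF readmission at 180 days.** The documents give no readmission rate. Assume that one minus Kaplan-Meier reads K, with constant and independent hazards for readmission and death. With a = −ln(1 − K), b = −ln(1 − M) and M the proportion dead:

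cumulative incidence = a/(a + b) × [1 − (1 − K)(1 − M)]

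For K = 0.35 and M = 0.108: a = 0.431 and b = 0.114; a/(a + b) = 0.790; 1 − 0.65 × 0.892 = 0.420; incidence = 0.790 × 0.420 = 0.332. Kaplan-Meier overstates by 1.8 points.

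Range over K, at M = 0.108:

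| 1 − Kaplan-Meier | True incidence | Excess |
|---|---|---|
| 25% | 23.7% | 1.3 points |
| 35% | 33.2% | 1.8 points |
| 45% | 42.8% | 2.2 points |

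The independence assumption can be relaxed. A simulation in which a gamma frailty (variance 1) drives both death and readmission, with 30% readmitted absent death and 10.8% dead, gives 29.0% by Kaplan-Meier against 27.7% observed, an excess of 1.3 points.

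**3. Effect on the treatment contrast.** Hold the readmission hazard equal in both arms (K = 0.35) and raise deaths from 10.8% to 15.8% in one arm.
- Independent hazards: Kaplan-Meier gives 35% in both arms and the death-censored hazard ratio is 1. In the arm with more deaths a/(a + b) = 0.431/(0.431 + 0.172) = 0.715 and 1 − 0.65 × 0.842 = 0.453, so the true incidence is 32.4% against 33.2%.
- Shared frailty, same simulation: the death-censored hazard ratio is 0.98 with 5 points more mortality and 0.96 with 10 points more. The cumulative-incidence ratios are 0.96 and 0.92.

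The hazard ratio is therefore nearly undisturbed. The Aalen-Johansen incidence is the correct quantity for risk, but it is lower where more patients die. It has to be read next to mortality.

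**4. In-hospital HF days.** The same simulation, with 10 days per readmission (assumed), the index stay not counted, and treatment changing death only:

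| 180-day mortality | HF days per patient | Days dead or in hospital |
|---|---|---|
| 10.8% | 3.82 | 13.9 |
| 15.8% | 3.61 | 18.6 |
| 20.8% | 3.39 | 23.6 |

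HF days fall as deaths rise, and the death-inclusive measure moves the other way. All inputs are assumed; the table shows direction and rough order only.

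**5. Time to discharge.** Under SAP 10.1.2 a patient who dies in hospital is censored at death. If the endpoint were analysed as a number of days under SAP 10.2.3, the day of death could stand as a short stay. The SAP does not say which applies or what the event is.

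**6. Imputation.** SAP 10.1.5 names missing follow-up values of primary and secondary endpoints without excluding deaths. Its closing text speaks of the composite endpoint but also says that results follow the structure of Tables 3 to 5, which include quality of life. The scope is ambiguous, and the wording permits imputation after death.

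**The case against.** The strongest reply is that no sentence in either document says deaths are censored or treated as missing in these endpoints. That is correct. The documents establish that a rule is absent and what the stated defaults do when applied literally.

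Second, Cox and log-rank with deaths censored already give a valid cause-specific comparison. That stands; what fails is Kaplan-Meier as an estimate of incidence, and the missing label on the hazard ratio.

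Third, Aalen-Johansen can itself look better in the arm with more deaths, as step 3 shows. That also stands, and is why it should not be reported alone.

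Fourth, the secondary analyses are exploratory, and SAP 2.2 also lists all-cause mortality, death or any re-hospitalisation at 180 days, and death or HF re-hospitalisation at 360 days. This limits the consequence but does not correct a mislabelled incidence or an imputed score after death.

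A reader might go further and infer that the plan systematically rewards the arm with more deaths, or will produce false claims of benefit. The documents do not support that. They give no arm-specific mortality, the p-values are not tested against a threshold, and the readmission hazard ratio barely moves. If the intervention lowers mortality as hypothesised, truncation of HF days works against it. A reader might also count every early death as a short stay; that requires treating time to discharge as a plain number, whereas SAP 10.1.2 sends it to the time-to-event approach.

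**Conclusion.** The point holds in a limited form. The SAP has no rule for death in its non-fatal secondary endpoints, and its defaults serve them poorly: Kaplan-Meier overstates HF readmission, HF days are truncated by death, and imputation is not confined to the living. The readmission overstatement is about 1.8 points (35% against 33.2%), or 1.3 to 2.2 points for Kaplan-Meier values of 25% to 45%. It rests on an assumed readmission level, constant independent hazards, and a 180-day death rate derived from the three-year figure. It is an error in the level within each arm, not a demonstrated bias in the treatment contrast. A larger gap follows if the 360-day death rate of about 20% is used, but HF re-hospitalisation alone is a 180-day endpoint.

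The primary endpoint is unaffected. Whether death should be ranked worst in quality of life is a choice of estimand on which statisticians differ; its absence is not an error.

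**What to change.** Add a short table to the SAP with one death rule per endpoint:

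- **HF re-hospitalisation.** Aalen-Johansen cumulative incidence with death competing, shown next to the Cox hazard ratio labelled cause-specific and the all-cause mortality result.
- **Time to discharge.** Define the event as discharge alive, with in-hospital death competing.
- **In-hospital HF days.** Keep the endpoint and add days alive and out of hospital to 180 and 360 days beside it.
- **Quality of life and functional status.** Restrict multiple imputation to patients alive at the time point and label the comparisons as among survivors. Death ranked worst can be an optional sensitivity analysis.

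The cost is SAP wording, modest programming and one or two more table rows. SAP 2.3 already names several sources for mortality, and time to discharge already needs the discharge date. If lengths of non-HF stays are not held to 360 days, the added measure can count HF stays only and be labelled so. Days alive and out of hospital will largely track mortality, so it belongs beside the HF-days result, not in its place.

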**Table 4 Quality of Life assessments at Baseline and Follow-up**

80

81

Table 4 Quality of Life (EQ-5D-3L) assessments at Baseline and Follow-up

82

Mobility – mean score (±SD)	XX±XX	XX±XX	XX±XX	X.XX	XX±XX	XX±XX	XX±XX	X.XX	XX±XX	X.XX
Self-care – mean score (±SD)	XX±XX	XX±XX	XX±XX	X.XX	XX±XX	XX±XX	XX±XX	X.XX	XX±XX	X.XX
Usual activities – mean score (±SD)	XX±XX	XX±XX	XX±XX	X.XX	XX±XX	XX±XX	XX±XX	X.XX	XX±XX	X.XX
Pain/discomfort – mean score (±SD)	XX±XX	XX±XX	XX±XX	X.XX	XX±XX	XX±XX	XX±XX	X.XX	XX±XX	X.XX
Anxiety/depression – mean score (±SD)	XX±XX	XX±XX	XX±XX		XX±XX	XX±XX	XX±XX	X.XX	XX±XX	X.XX
Quality of life assessed at 180 days	N= xx	N= xx	N= xx		N= xx	N= xx	N= xx		N= xx	
VAS scale – mean score (±SD)	XX±XX	XX±XX	XX±XX	X.XX	XX±XX	XX±XX	XX±XX	X.XX	XX±XX	X.XX
Mobility – mean score (±SD)	XX±XX	XX±XX	XX±XX	X.XX	XX±XX	XX±XX	XX±XX	X.XX	XX±XX	X.XX
Self-care – mean score (±SD)	XX±XX	XX±XX	XX±XX	X.XX	XX±XX	XX±XX	XX±XX	X.XX	XX±XX	X.XX
Usual activities – mean score (±SD)	XX±XX	XX±XX	XX±XX	X.XX	XX±XX	XX±XX	XX±XX	X.XX	XX±XX	X.XX
Pain/discomfort – mean score (±SD)	XX±XX	XX±XX	XX±XX	X.XX	XX±XX	XX±XX	XX±XX	X.XX	XX±XX	X.XX
Anxiety/depression – mean score (±SD)	XX±XX	XX±XX	XX±XX	X.XX	XX±XX	XX±XX	XX±XX	X.XX	XX±XX	X.XX
Quality of life assessed at 360 days	N= xx	N= xx	N= xx		N= xx	N= xx	N= xx		N= xx	
VAS scale – mean score (±SD)	XX±XX	XX±XX	XX±XX	X.XX	XX±XX	XX±XX	XX±XX	X.XX	XX±XX	X.XX
Mobility – mean score (±SD)	XX±XX	XX±XX	XX±XX	X.XX	XX±XX	XX±XX	XX±XX	X.XX	XX±XX	X.XX
Self-care – mean score (±SD)	XX±XX	XX±XX	XX±XX	X.XX	XX±XX	XX±XX	XX±XX	X.XX	XX±XX	X.XX
Usual activities – mean score (±SD)	XX±XX	XX±XX	XX±XX	X.XX	XX±XX	XX±XX	XX±XX	X.XX	XX±XX	X.XX
Pain/discomfort – mean score (±SD)	XX±XX	XX±XX	XX±XX	X.XX	XX±XX	XX±XX	XX±XX	X.XX	XX±XX	X.XX
Anxiety/depression – mean score (±SD)	XX±XX	XX±XX	XX±XX	X.XX	XX±XX	XX±XX	XX±XX	X.XX	XX±XX	X.XX

83

84

85 It is expected that the Kansas city  
86 will be reported in secondary

87 **Figure 2 KCCQ summary change**

[figure not shown]
88

89

90

91

92

93

94

95

96

97

98

99

100

101 KCCQ summary score ranges from 0 to 100 with higher scores indicating better health status. An increase of 10 points or more from baseline  
102 corresponds to moderate or great clinical improvement.

103

104

105

106 It is expected that additional  
107 reported in secondary publications:

**Change from baseline**

Intervention arm	xx±xx	xx±xx	xx±xx
Standard of care arm	xx±xx	xx±xx	xx±xx
95 % CI for difference	(xx.xx – xx.xx)	(xx.xx – xx.xx)	(xx.xx – xx.xx)

biomarkers will be

108

109 **Table 5 Baseline and follow-up biomarkers assessments.**

110

111

112 Table 5 Baseline and follow-up biomarkers assessments.

113

114

115

	Intervention arm				Standard of care arm				Intervention vs standard of care	
	Baseline (N=)	Follow-up (N=)	Change FU vs Baseline	p-value	Baseline (N=)	Follow-up (N=)	Change FU vs Baseline	p-value	Mean difference of the change	p-value
-xx (±SD)	xx±xx	xx±xx	xx±xx	x.xx	xx±xx	xx±xx	xx±xx	x.xx	xx±xx	x.xx
-xx (±SD)	xx±xx	xx±xx	xx±xx	x.xx	xx±xx	xx±xx	xx±xx	x.xx	xx±xx	x.xx
-xx (±SD)	xx±xx	xx±xx	xx±xx	x.xx	xx±xx	xx±xx	xx±xx	x.xx	xx±xx	x.xx
-xx (±SD)	xx±xx	xx±xx	xx±xx	x.xx	xx±xx	xx±xx	xx±xx	x.xx	xx±xx	x.xx
-xx (±SD)	xx±xx	xx±xx	xx±xx	x.xx	xx±xx	xx±xx	xx±xx	x.xx	xx±xx	x.xx

116

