64 **iv. Endpoint tables**

65 The following table will be produced and

66 Table 3 will be provided in the main publication:

67

68 **Table 3: Primary and secondary endpoint events**

Event	Intervention arm (N=)	Standard of care arm (N=)	Hazard Ratio (95%CI)	p-value
Primary composite endpoint – no. (%)†	xx (xx%)	xx (xx%)	x.xx (x.xx-x.xx)	x.xx
All-cause mortality — no. (%)	xx (xx%)	xx (xx%)	x.xx (x.xx-x.xx)	x.xx
Heart failure hospitalization – no. (%)	xx (xx%)	xx (xx%)	x.xx (x.xx-x.xx)	x.xx
Secondary endpoints – no. (%)	xx (xx%)	xx (xx%)	x.xx (x.xx-x.xx)	x.xx
All-cause mortality at 180 days.— no. (%)	xx (xx%)	xx (xx%)	x.xx (x.xx-x.xx)	x.xx
Heart failure hospitalization – no. (%)	xx (xx%)	xx (xx%)	x.xx (x.xx-x.xx)	x.xx
Death or re-hospitalization at 180 days. — no. (%)	xx (xx%)	xx (xx%)	x.xx (x.xx-x.xx)	x.xx
Need for ICU admission during initial hospitalization — no. (%)	xx (xx%)	xx (xx%)	x.xx (x.xx-x.xx)	x.xx
Acute coronary syndrome during initial hospitalization — no. (%)	xx (xx%)	xx (xx%)	x.xx (x.xx-x.xx)	x.xx
Symptomatic hypotension during initial hospitalization — no. (%)	xx (xx%)	xx (xx%)	x.xx (x.xx-x.xx)	x.xx
B-type natriuretic peptide (BNP) level – ng/l (±SD)	xx±xx	xx±xx	x.xx (x.xx-x.xx)	x.xx
at 48 hours	xx±xx	xx±xx	x.xx (x.xx-x.xx)	

69

	Intervention arm				Standard of care arm				Intervention vs standard of care	
	Baseline (N=)	Follow-up (N=)	Change FU vs Baseline	p-value	Baseline (N=)	Follow-up (N=)	Change FU vs Baseline	p-value	Mean difference of the change	p-value
at discharge										
Creatinine level – µmol/l (±SD)		XX±XX			XX±XX				x.xx (x.xx-x.xx)	
at 48 hours										
at discharge		XX±XX			XX±XX				x.xx (x.xx-x.xx)	
Changes in circumferences of both legs during initial hospitalization – cm (±SD)		XX±XX			XX±XX				x.xx (x.xx-x.xx)	
Blood pressure course over the first 6 days – mmHg (±SD)		XX±XX			XX±XX				x.xx (x.xx-x.xx)	
Time to disappearance of a third heart sound (if present initially) – days (±SD)		XX±XX			XX±XX				x.xx (x.xx-x.xx)	
Quality of life assessed at 90 days (±SD)	N= xx	N= xx	N= xx	x.xx	N= xx	N= xx	N= xx	x.xx	N= xxx	
Total triAS scale – mean score (±SD)	xx±xx	xx±xx	xx±xx	x.xx	xx±xx	xx±xx	xx±xx	x.xx	xx±xx	x.xx
Fractures due to fall within 180 days and 360 days – no. (%)		xx (xx%)			xx (xx%)				x.xx (x.xx-x.xx)	
Death or HF re-hospitalization at 360 days – no. (%)		xx (xx%)			xx (xx%)				x.xx (x.xx-x.xx)	

70

71

72

73

74

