**iii. Continuous scale data**

Continuous data will be compared Intervention arm vs Standard of care using Mann–Whitney U test with two-sided p-values.

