#### i. Brief summary of adverse events

The following AEs will be collected:

- Headaches
- Dizziness
- Fall
- Creatinine increase > 30% of baseline
- Hypokalemia < 3.5 mmol/l
- Hyperkalemia > 5 mmol/l
- Arrhythmia requiring therapy
- Systolic arterial hypotension < 80 mm Hg over 30 minutes
- Acute coronary syndrome
- Transfer to the intensive care unit
- Cardiopulmonary resuscitation

The following SAEs will be collected

- In-patient hospitalization
- Prolongation of existing hospitalization
- Life threatening event
- Death

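### Table 5 pairs a raw mean difference in biomarker change with a rank test, and Table 3 puts BNP and creatinine levels under a hazard ratio; one baseline-adjusted log-scale analysis would repair both

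*Combined protocol and SAP*

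**What the plan says.** **Table 5** (SAP 10.1.4, Endpoint tables) covers additional biomarkers meant for secondary publications. Its rows are unnamed placeholders. Baseline, follow-up and change are each mean ± SD, followed by a between-arm "Mean difference of the change" and a p-value. The table names no test and prints no between-arm confidence interval.

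**Method.** SAP 10.2.3 states: "Continuous data will be compared Intervention arm vs Standard of care using Mann–Whitney U test with two-sided p-values". SAP 10.1.3 instead sends other endpoints, novel biomarkers included, to the approach for secondary endpoints. SAP 10.1.2 takes that from the primary endpoint, which means Cox regression, Kaplan-Meier and log-rank.

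**Table 3.** The BNP row is labelled "B-type natriuretic peptide (BNP) level – ng/l (±SD" with the bracket closed, and has entries at 48 hours and at discharge. Creatinine has the same layout. The effect column of this table is a hazard ratio with 95% CI. This fits SAP 2.2 in one respect: the secondary endpoints are levels of BNP and creatinine at those two times, not changes.

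**Status.** SAP 6.6.4 treats secondary analyses as exploratory and does not read their p-values against a threshold.

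**The concern.** BNP enters the trial at 500 ng/l or more (350 at a BMI of 35 or more) with no ceiling (protocol 4.1). Concentrations bounded below and open above can be expected to be right-skewed, and other cardiac biomarkers may behave the same way. On the raw scale a high starting value carries great weight, so a mean difference of change can be set by a few patients. A rank test beside it addresses a different quantity, so estimate and p-value need not tell the same story.

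In Table 3 the problem is more basic. A BNP or creatinine level at a fixed time has no hazard, so the column cannot be filled as headed, and the strongest predictor of the follow-up value, its own baseline, goes unused.

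The stake is moderate. A faster and larger fall in BNP is a stated hypothesis in both the protocol summary and the SAP synopsis. Because SAP 6.6.4 drops the significance threshold, the effect estimate has to carry the interpretation, and the estimate is the part that is poorly specified.

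**Working it through.** **The plan's own figure.** There is no biomarker power or sample-size statement to reproduce. The only figure is 385 per arm for the primary endpoint, and its control event rate is not given. It back-solves to about 50% versus 40%: (1.960 + 0.842)² × (0.25 + 0.24) / 0.10² = 384.6. It serves here only as a realistic group size.

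**Inputs from the documents.** Tests are two-sided ("All hypothesis testing will be two-tailed", protocol 8.2). The 5% level is taken from protocol 8.2 and the sample-size section ("statistically significant at the 5%-level"). The BNP entry floor is 500 ng/l.

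**Inputs assumed, because the documents give none.** Baseline is log-normal with median 1000 ng/l before truncation at 500. The treatment effect is multiplicative.
- Set A: 350 per arm, log-SD of baseline 0.7–0.9, log-SD of the follow-up/baseline ratio 0.6–0.8, both arms falling to 60% before the treatment effect.
- Set B: 385 per arm, log-SDs 0.6–1.0 and 0.5–0.7, control ratio 0.65.

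**Step 1: weight of a high baseline.** A fall from 6000 to 3000 is a change of −3000. A fall from 600 to 300 is −300, a tenth as much. On the log scale both are ln 0.5 = −0.693. Under set B the 5% of patients with the highest baseline supply 28–61% of the variance of raw change (this range includes runs with 300 per arm). Under set A they supply 35–52%.

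**Step 2: log-scale power.** The model is log(follow-up) = a + b·log(baseline) + θ·arm, and exp(θ) is the ratio of geometric means. With residual log-SD s, z = |ln R| / (s√(2/n)) and power ≈ Φ(z − 1.96). For R = 0.85, |ln R| = 0.1625. At n = 350:
- s = 0.6: z = 0.1625 / 0.04536 = 3.58, power 95%.
- s = 0.8: z = 0.1625 / 0.06047 = 2.69, power 77%.

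**Step 3: set A by simulation, R = 0.85.**
- t-test on raw change, the test that matches the tabulated mean: 38–69%.
- Mann-Whitney on raw change: 57–81%.
- Mann-Whitney on the level: 53–71%.
- Log ANCOVA: 77–95%, as in step 2.

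The gain over the rank test on raw change is 95 − 81 = 14 points at the upper ends and 77 − 57 = 20 at the lower ends. Over the rank test on the level it is about 24 points (77 − 53; 95 − 71). The two raw-change tests disagree at 5% in 19–29% of trials.

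**Step 4: set B by simulation, R = 0.85, 800 trials per setting (power in %).**

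| log-SD baseline / ratio | t, raw change | Mann-Whitney, raw change | Mann-Whitney, level | log ANCOVA | t and rank disagree |
|---|---|---|---|---|---|
| 0.6 / 0.5 | 91.0 | 95.5 | 87.6 | 99.5 | 6.2 |
| 0.6 / 0.7 | 66.8 | 80.5 | 72.1 | 89.5 | 20.0 |
| 0.8 / 0.5 | 81.0 | 94.0 | 79.4 | 99.4 | 15.5 |
| 0.8 / 0.7 | 55.6 | 74.1 | 65.1 | 88.2 | 26.8 |
| 1.0 / 0.5 | 67.2 | 90.9 | 69.2 | 99.0 | 25.1 |
| 1.0 / 0.7 | 45.6 | 68.5 | 53.4 | 88.8 | 30.9 |

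The gain over the rank test on raw change runs from 99.5 − 95.5 = 4 to 88.8 − 68.5 = 20 points. It is small where power is already near its ceiling. Over the rank test on the level it runs from 99.5 − 87.6 = 12 to 88.8 − 53.4 = 35 points. At R = 0.90 log ANCOVA has 53–84%, against 40–67% for the rank test on raw change and 29–52% for the rank test on the level.

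**Step 5: agreement in direction.** At R = 0.90 the mean difference and the rank test point opposite ways in 1–12% of trials, and at 0.85 in 0–6% (385 or 300 per arm). With no true effect they disagree at 5% in 4–7%.

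**The case against.** The strongest reply is that little depends on this. The analyses are exploratory, Table 5 concerns unnamed biomarkers for later papers, and power at 5% is measured against a threshold that SAP 6.6.4 disclaims. All of that stands and keeps the point small. It does not rescue the estimate, which is what remains once the threshold is gone.

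A second reply is that for the BNP level under Mann-Whitney, taking logs leaves the p-value unchanged, and extreme values cannot drive a rank test. This is correct. The power gain in Table 3 comes from adjusting for baseline, not from the logarithm. The log scale supplies a usable effect measure.

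It could also be said that the primary model already includes serum creatinine and is stratified by the randomization factors (SAP 6.1 and 6.6.2). Carried over through 10.1.2, that would still be a Cox model and would give no comparison of levels.

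Several stronger readings are tempting but unsupported:
- A reader might infer that Table 3 also reports a mean difference of BNP change. It shows levels. The change header in the middle of that table sits with quality-of-life rows and looks like Table 4's header displaced in extraction.
- A reader might infer that Table 5 could print p < 0.05 beside an interval that includes zero. It prints no between-arm interval. The one nearby belongs to the KCCQ figure.
- A reader might take "Creatinine increase > 30% of baseline" as evidence that the plan wants biomarkers compared proportionally. That is an adverse-event threshold for individual patients and says nothing about comparing arms.
- A reader might treat the power loss as a fact about this trial. It follows from assumed skew and an assumed proportional effect.

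**Conclusion.** The point holds in limited form, as a worthwhile improvement. For Table 5, if 10.2.3 governs, a raw mean difference stands beside a rank p-value. Change in original units is the natural reading of change ± SD, although the SAP does not use those words, and 10.1.3 points to a different method. For Table 3, the hazard ratio cannot apply to a BNP or creatinine level, whatever the distribution.

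The mismatch between estimate and test, and the wrong effect measure, need no simulation. The size of the gain does. At a true ratio of 0.85 it is roughly 14–20 points over the rank test on raw change under set A and 4–20 under set B, and about 24 (set A) or 12–35 (set B) over the rank test on the level. If treatment removed a fixed number of ng/l, with scatter that did not grow with baseline, the gain would shrink or vanish. That case is not quantified here. The primary endpoint is unaffected.

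**What to change.** For the biomarkers of Table 5 and the BNP and creatinine rows of Table 3:
- Analyse log follow-up with log baseline and arm in the model (ANCOVA).
- Report the ratio of geometric means with its 95% CI, and the p-value from that same model.
- Show median (IQR) per arm at each time, a format the Table 1 footnote already allows.
- Drop the raw mean difference of change from Table 5, and remove these rows from the hazard-ratio column of Table 3.
- Amend 10.1.2, 10.1.3 and 10.2.3 so that one method applies to continuous biomarkers and the time-to-event approach is confined to time-to-event endpoints.

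The cost is SAP wording and table shells, with no new data, visits or patients. The small downside is that a ratio is less familiar to readers than a difference in ng/l.
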